Blood samples will be collected throughout the trial for the purpose of evaluating the endocrine profile and clinical chemistry and haematology parameters. AMH, thyroid-stimulating hormone (TSH), and prolactin concentrations will be assessed at screening whereas estradiol and progesterone concentrations will be assessed on stimulation days 1 and 6 and at end-of-stimulation. Clinical chemistry and haematology parameters will be assessed at screening and at end-of-trial.

Symptoms of OHSS will be recorded, and all OHSS events will be graded according to Golan's classification system. Early OHSS is defined as OHSS with onset ≤ 9 days after triggering of final follicular maturation, and late OHSS is defined as OHSS with onset >9 days after triggering of final follicular maturation.

If trial procedures and/or assessments are to be performed on Sundays, public holidays or outside the opening hours of the clinic, the procedures and/or assessments can be postponed to the upcoming weekday (maximum one day after original visit schedule).

All subjects with an ongoing pregnancy will be followed until delivery for collection of information on pregnancy outcome. Data on neonatal health, including any congenital anomalies, at birth and at 4 weeks after birth will be collected and reported separately.

NUMBER OF SUBJECTS

The total number of subjects to be randomised is approximately 300 (150 subjects to treatment with FE 999049 and 150 subjects to treatment with GONAL-F).

CRITERIA FOR INCLUSION / EXCLUSION

Inclusion Criteria

1. Signed and dated Informed Consent Form for participation in the trial, obtained before any trial-related procedures.
2. Signed and dated Informed Consent Form for data collection on the neonate, obtained before randomisation to treatment.
3. In good physical and mental health in the judgement of the investigator.
4. Chinese pre-menopausal female between the ages of 20 and 40 years; at least 20 years (including the 20th birthday) when signing the informed consent and no more than 40 years (up to the day before the 41st birthday) at the time of randomisation.
5. Eligible for ovarian stimulation with a dose equivalent to 150 IU GONAL-F or 225 IU GONAL-F, as judged by the investigator.
6. Body mass index (BMI) between 17.5 and 32.0 kg/m² (both inclusive) at screening.

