Subjects will be screened within 90 days prior to randomisation for compliance with the inclusion and exclusion criteria. A long GnRH agonist protocol will be used for pituitary downregulation; treatment with GnRH agonist (triptorelin acetate, DECAPEPTYL, Ferring), 0.1 mg/day, will be initiated in the mid-luteal phase (i.e. cycle day 21-24) of the subject's menstrual cycle. A minimum of 10 days with GnRH agonist administration should be ensured prior to confirmation of downregulation, which is defined as fulfilling the following criteria: 1) menstrual bleeding, 2) shed endometrium with a thickness <5 mm observed by transvaginal ultrasound, and 3) no ovarian follicles ≥10 mm (including cysts that cannot be punctured prior to stimulation) observed by transvaginal ultrasound. In case achievement of downregulation is doubtful or it is deemed helpful, serum estradiol is to be measured (<50 pg/mL or 180 pmol/L; local laboratory). Once downregulation is confirmed, randomisation and start of stimulation must occur within 7 days. Treatment with GnRH agonist is to be continued after confirmation of downregulation and throughout the stimulation period. If the subject has not experienced menstrual bleeding at the first assessment of confirmation of downregulation, a urinary pregnancy test is to be performed. If the subject is not pregnant, treatment with GnRH agonist will be continued and subsequent visit(s) for confirmation of downregulation will be scheduled according to local practice. If downregulation is not achieved after 28 days, treatment with GnRH agonist will be stopped and the subject will be discontinued from the trial as a screening failure.

Randomisation will be stratified according to the investigator's assessment of an appropriate starting dose (10 µg FE 999049 / 150 IU GONAL-F or 15 µg FE 999049 / 225 IU GONAL-F). Randomisation to FE 999049 and GONAL-F will be in a 1:1 ratio within each stratum. Subjects randomised to FE 999049 will receive a daily starting dose of 10 µg or 15 µg which will be fixed for the first five stimulation days. Based on the subject's ovarian response, the dose may be increased or decreased by 5 µg, with dose adjustments implemented not more frequently than once every 2 days. The minimum FE 999049 dose is 5 µg and the maximum FE 999049 dose is 20 µg. Subjects randomised to GONAL-F will receive a daily starting dose of 150 IU or 225 IU which will

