4 SELECTION OF TRIAL POPULATION

4.1 Trial Population

4.1.1 Inclusion Criteria

Subjects must meet all of the criteria below to be eligible for participation on this trial.

1. Signed and dated Informed Consent Form for participation in the trial, obtained before any trial-related procedures.
2. Signed and dated Informed Consent Form for data collection on the neonate, obtained before randomisation to treatment.
3. In good physical and mental health in the judgement of the investigator.
4. Chinese pre-menopausal female between the ages of 20 and 40 years; at least 20 years (including the 20th birthday) when signing the informed consent and no more than 40 years (up to the day before the 41st birthday) at the time of randomisation.
5. Eligible for ovarian stimulation with a dose equivalent to 150 IU GONAL-F or 225 IU GONAL-F, as judged by the investigator.
6. Body mass index (BMI) between 17.5 and 32.0 kg/m² (both inclusive) at screening.
7. Infertile women diagnosed with tubal infertility, unexplained infertility, endometriosis stage I/II or with partners diagnosed with male factor infertility, eligible for in vitro fertilisation (IVF) or intracytoplasmic sperm injection (ICSI) using fresh or frozen ejaculated sperm from male partner or sperm donor.
8. Infertility for at least one year before randomisation for subjects <35 years or for at least 6 months for subjects ≥35 years (criteria not applicable in case of tubal or severe male factor infertility).
9. Regular menstrual cycles of 24-35 days (both inclusive), presumed to be ovulatory.
10. Transvaginal ultrasound documenting presence and adequate visualisation of both ovaries, without evidence of significant abnormality (e.g. no endometrioma greater than 3 cm, and no enlarged ovaries or ovarian cyst not due to polycystic ovarian syndrome, which would contraindicate the use of gonadotropins) and normal adnexa (e.g. no hydrosalpinx) within 1 year prior to randomisation. Both ovaries must be accessible for oocyte retrieval.
11. Early follicular phase (cycle day 2-4) serum levels of follicle-stimulating hormone (FSH) between 1 and 15 IU/L (results obtained within 3 months prior to randomisation).
12. Serum anti-Müllerian hormone (AMH) concentration of ≤35 pmol/L at screening.
13. Confirmation of downregulation prior to randomisation, defined as fulfilling all of the following criteria:
 - a. menstrual bleeding
 - b. shed endometrium with a thickness <5 mm observed by transvaginal ultrasound

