6.3 Downregulation

Subjects will attend the downregulation visit on day 21-24 of their menstrual cycle.

The following must take place prior to initiation of pituitary downregulation:

- Ensure that the subject is still eligible for participation in the trial
- Check those inclusion and exclusion criteria that were not possible during screening
- Urinary pregnancy test – must be negative
- Recording of use of any concomitant medication
- Recording of adverse events

Once the above has been completed, the following must be performed by the trial medication delegate:

- Dispensing and administration of GnRH agonist [the first administration of GnRH agonist takes place at the clinic and can be done by either the trial medication delegate or the subject under supervision by the trial medication delegate]

The GnRH agonist should preferably be administered at the same time each day during the downregulation period and the timing of the GnRH agonist administrations should be aligned with the IMP administrations during the stimulation period.

Finally, this must be done before the subject leaves the clinic:

- In the first 30 min following the GnRH agonist administration, the trial medication delegate (or another qualified trial staff) must observe the subject's general health with emphasis on symptoms of an acute allergic reaction.
- Instruct the subject to administer the GnRH agonist at a daily dose of 0.1 mg until the end-of-stimulation visit.

After the downregulation visit, the next visit must be scheduled to ensure a minimum of 10 days with GnRH agonist administration.

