9.6 Statistical Analysis

9.6.1 General Considerations

Non-inferiority comparison for the primary endpoint will be performed for both the FAS and the PP analysis set. Other efficacy analyses will be performed for the FAS only. All descriptions of safety data (including the secondary endpoint on OHSS) will be based on the safety analysis set.

Missing data will, in general, not be imputed. For subjects without oocyte retrieval, the number of oocytes, fertilised oocytes, and embryos will be regarded as zero. For pregnancy endpoints, lack of data will be interpreted as a negative pregnancy, unless a subsequent pregnancy endpoint is confirmed to be positive. Missing endocrine values of stimulation day 1 will, when used as covariate, be imputed by the mean of all non-missing values for this visit.

All statistical analyses will be detailed in a Statistical Analysis Plan which will be issued as a separate document and finalised before FPFV.

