The investigator (or the person delegated by the investigator) will obtain a freely given written consent from the child-custody holders, i.e. the subject and the subject's partner in case of joint custody. The child-custody holders must be given ample time before the consent is obtained. The Informed Consent Form must be signed and dated by the child-custody holders and the investigator who has provided information to the child-custody holders. Written consent by the child-custody holders regarding collection of pregnancy outcome data on the neonate must be obtained before the subject is randomised and preferably at the time of obtaining written consent by the subject regarding participation in the trial.

The investigator will explain that the child-custody holders are completely free to refuse to consent to this data collection or to withdraw consent at any time, without any consequences and without the need to justify their decision.

The child-custody holders will receive copies of the signed and dated Informed Consent Forms before randomisation to treatment.

The child-custody holders will be informed that the monitor(s), quality assurance auditor(s) mandated by Ferring, ethics committee representatives or regulatory authority inspector(s), in accordance with applicable regulatory requirements, may review the neonate's source records and data. Data protection will be handled in compliance with national / local regulations.

Partner Privacy Notice

The privacy notice explains the possibility that the partner's personal information (such as name, infertility diagnosis, etc.) may be included in the subject's medical record.

The partner will be informed that the monitor(s), quality assurance auditor(s) mandated by Ferring, ethics committee representatives or regulatory authority inspector(s), in accordance with applicable regulatory requirements, may have access to the partner's personal information (such as name, infertility diagnosis, etc.). Protection of personal data will be handled in accordance with national / local regulations. Ferring will not collect, use or store any of the partner's personal data. The partner privacy notice must be given to the partner before the subject is randomised.

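### Neonatal-data consent is an entry condition that may be signed as late as randomisation, after 10 to 35 days of GnRH agonist, while Section 14.5 has custody holders told that refusal carries no consequences

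*Combined protocol and SAP*

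**What the plan says.** Two consents are entry conditions, with different deadlines. Criterion 1 asks for "Signed and dated Informed Consent Form for participation in the trial, obtained before any trial-related procedures". Criterion 2 asks for "Signed and dated Informed Consent Form for data collection on the neonate, obtained before randomisation to treatment". Section 4.1.1 makes both binding: "Subjects must meet all of the criteria below to be eligible for participation on this trial".

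Section 14.5 identifies the signatories of the second form as the child-custody holders, meaning the woman and, under joint custody, her partner. On timing, it says the consent "must be obtained before the subject is randomised and preferably at the time of obtaining written consent by the subject" regarding participation. It then has the investigator explain that the custody holders are "completely free to refuse to consent to this data collection or to withdraw consent at any time, without any consequences".

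The paragraph of Section 14.5 on the woman's own consent makes a similar promise, but limits it to her further care. The neonatal paragraph has no such limit.

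Randomisation takes place on stimulation day 1, after downregulation is confirmed (Sections 4.2.2 and 6.5.1). Section 3.1.2 states: "A minimum of 10 days with GnRH agonist administration should be ensured prior to confirmation of downregulation".

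**The concern.** Two problems meet here.

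The first is the statement made to the couple. A woman whose neonatal-data form is unsigned cannot be randomised, so refusal costs her entry to the trial. An investigator who applies criterion 2 cannot also say truthfully, without qualification, that refusal has no consequences.

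The second is the deadline. Because it is randomisation and not the start of the agonist, the plan permits the decisive refusal to come when the woman is already downregulated. By then she has had daily injections whose hypoestrogenic reactions and cyst risk are acknowledged in Section 1.3. She cannot be re-screened (Section 4.5), and she may not continue therapy outside the trial with trial-supplied products (Section 4.3.2). The partner's refusal alone can have this effect under joint custody.

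At stake are an avoidable screening failure after drug exposure and the accuracy of a consent statement. The trial's efficacy conclusion is not at stake.

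**Working it through.** The plan gives no figure for agonist exposure at the consent deadline, so there is none to reproduce. It follows from the protocol's own windows.

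**Inputs**
- Minimum agonist days before confirmation of downregulation: 10 (Section 3.1.2).
- Limit for achieving downregulation: 28 days (Sections 3.1.2 and 6.4). I read this as counted from the first agonist dose, which is the natural reading but is not spelled out.
- Confirmation to randomisation: at most 7 days (Sections 3.1.2 and 4.2.2). Section 6.4 allows both on the same day, so the minimum is 0.
- The agonist continues between confirmation and randomisation (Section 3.1.2).

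**Exposure at the latest permitted signing** = days to confirmation + days from confirmation to randomisation
- Lower bound: 10 + 0 = 10 days.
- Upper bound: 28 + 7 = 35 days.
- If the general one-day postponement for closed clinic days (Section 3.1.2) is added: 35 + 1 = 36 days.

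**Does any other section bring the deadline forward?**
- Table 6-1 has one row for written informed consent, marked at screening. It does not say which form.
- Section 6.2 lists a consent obtained before any trial-related procedure, which is the timing of criterion 1. It also calls for the criteria that can be checked at screening.
- Section 6.3, before the first agonist dose, says: "Check those inclusion and exclusion criteria that were not possible during screening". It does not name the neonatal form.
- Section 6.5.1 repeats that generic check on stimulation day 1, after the agonist phase, and does not name the form either.

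Under criterion 2 as worded, a form still unsigned at screening or at the downregulation visit is not yet a failed criterion, because the deadline has not passed. These checks prompt earlier signing but do not compel it.

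**Is the no-consequences statement compatible with criterion 2?** Refusal means criterion 2 is unmet. All criteria must be met, so there is no randomisation and no trial stimulation. That is a consequence. The statement would be compatible if limited to further care, as it is for the woman's own consent. The conflict concerns refusal before randomisation; the plan states no effect on the woman's treatment if consent is withdrawn afterwards.

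**The case against.** The strongest reply is that late signing is not the planned flow. Section 14.5 prefers signing with the main consent, the flow chart places consent at screening, a signed form can be checked at screening, and Section 6.3 provides another check before the first agonist dose. A site would have to pass over all of these. This stands as to likelihood: late refusal should be uncommon, and 35 days is the far edge of two windows. It does not remove the permission, which both criterion 2 and Section 14.5 give.

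A second reply is that refusing the main consent also prevents entry and nobody calls that contradictory, so the wording is only loose. That is fair up to a point, since most of the conflict disappears once the missing limitation is added. The consent form itself is not among the documents reviewed and may be worded better. Section 14.5 as written still needs correcting.

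A reader might go further and infer that a site following Section 14.5 could randomise a woman without this consent, and that her missing birth outcome would then count as no live birth. The documents do not support either step:
- Section 14.5 itself requires the consent before randomisation, so randomising without it breaches both that section and criterion 2.
- The rule in Section 9.6.1, "For pregnancy endpoints, lack of data will be interpreted as a negative pregnancy", is written for pregnancy endpoints. Section 9.6.3 lists these as positive βhCG and clinical, vital and ongoing pregnancy.
- Live birth is a separate follow-up endpoint (Section 2.2). Section 9.8 carries over the method of comparison and does not say that missing live births are failures.

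**Conclusion.** The point holds as a minor inconsistency with a participant-protection side. An entry condition may be settled after 10 to 35 days of GnRH agonist, and the explanation prescribed for the custody holders does not match the effect of refusing. The upper figure assumes that the 28 days run from the first agonist dose and that both windows are used in full.

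The number of women affected cannot be estimated. The documents give no refusal rate, and only refusals first made after the agonist has started would count; a refusal at screening involves no agonist exposure. A reader might also be tempted to apply an assumed rate to the 300 planned subjects. That is the number to be randomised, and under the plan women without this consent are not among them.

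The primary endpoint, alpha and power are unaffected.

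**What to change.** - **Criterion 2 (synopsis and Section 4.1.1) and Section 14.5:** require the neonatal-data consent to be signed before the first GnRH agonist administration, in place of before randomisation.
- **Section 6.3:** name the signed neonatal-data form among the checks completed before that administration.
- **Section 14.5 and, if needed, the consent form:** say that refusal before that point precludes trial entry but does not affect further care, and that later withdrawal does not affect the woman's own participation. Criterion 2 is then judged once, at signature, and a later withdrawal does not reopen eligibility.

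The cost is wording in four places and possibly the consent form, with no added visit, procedure or change of treatment. The one downside is that couples who would have decided later must decide before the agonist starts.

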ICMJE	International Committee of Medical Journal Editors
ICSI	intracytoplasmic sperm injection
IMP	investigational medicinal product
IRT	interactive response technology
IVF	in vitro fertilisation
LH	luteinising hormone
LLOQ	lower limit of quantification
LPLV	last patient last visit
MedDRA	Medical Dictionary for Regulatory Activities
NIMP	non-investigational medicinal product
NLM	National Library of Medicine
NMPA	National Medical Products Administration

OHSS	ovarian hyperstimulation syndrome
OR	oocyte retrieval
PP	per-protocol
PT	preferred term
rFSH	recombinant follicle-stimulating hormone
SAE	serious adverse event
SOC	system organ class
SUSAR	suspected, unexpected serious adverse reaction
TSH	thyroid-stimulating hormone
US	ultrasound
ULOQ	upper limit of quantification
UTN	Universal Trial Number
WHO	World Health Organization

Company Names

Ferring will be used as abbreviation for Ferring Pharmaceuticals.

1 INTRODUCTION

1.1 Background

Follitropin delta (FE 999049) is a novel human recombinant follicle-stimulating hormone (rFSH) derived from a human cell line (PER.C6[®]). It is intended for the development of multiple follicles during controlled ovarian stimulation in women undergoing assisted reproductive technologies (ART) such as an in vitro fertilisation (IVF) or intracytoplasmic sperm injection (ICSI) cycle. The first Marketing Authorisation approval of FE 999049 (REKOVELLE) was obtained by the European Commission in December 2016. A Biological License Application was submitted to the National Medical Products Administration in China in December 2020 for approval of FE 999049 with a proposed dosing regimen based on each woman's serum anti-Müllerian hormone (AMH) concentration and her body weight.

As of 01 April 2023, a total of 14 clinical trials have been completed as part of the FE 999049 global development programme: five phase 1 trials, two phase 2 trials, and seven phase 3 trials. A total of 4,878 subjects have been included in the completed clinical trials, of whom 3,269 subjects were exposed to FE 999049. Out of the seven phase 3 trials, trial 000145 has been conducted in China and included a total of 759 Chinese IVF or ICSI subjects, of whom 378 subjects were exposed to FE 999049. These subjects received an individualised dose in accordance with their serum AMH concentration and body weight, with a maximum dose of 12 µg, and were treated with a gonadotropin-releasing hormone (GnRH) antagonist protocol.¹ The majority of clinical trial data with FE 999049 has been generated with the GnRH antagonist protocol.

An essential part of ovarian stimulation involves concomitant treatment with GnRH analogues to prevent premature luteinisation and ovulation,² which can be achieved via two different approaches: pituitary desensitisation with prolonged daily administration of a GnRH agonist or instant blockade of the pituitary luteinising hormone (LH) secretion with a GnRH antagonist.^{3,4,5} Both treatments are effective in preventing premature LH surges^{4,6,7} and comparable in respect of clinical outcomes, such as number of oocytes retrieved and live birth rates.^{5,8} Nonetheless GnRH analogues differ in their safety profile,^{9,10} GnRH agonist treatment being associated with adverse drug reactions related to hypoestrogenism and with higher incidence of OHSS compared with GnRH antagonist treatment, especially in predicted normal to high responders.^{5,8,11}

Differently from the algorithmic dosing of FE 999049, which is based on each subject's serum AMH concentration and body weight, the starting dose in conventional dosing of rFSH is commonly based on age, previous IVF outcomes, and markers of ovarian reserve such as antral follicle counts and circulating AMH, follicle-stimulating hormone (FSH), and estradiol concentrations.^{12,13} A starting dose of 150 or 225 IU rFSH is applied in women with anticipated normal ovarian response, 150 IU being applied in women of younger age and expected to have a robust response, and 225 IU being applied in women of older age or in women expected to have a less robust response.^{14,15} The dose is fixed for the initial days of stimulation, followed by the possibility for subsequent dose adjustments.^{14,16}

Previous trials comparing efficacy and safety of a GnRH antagonist protocol with a long GnRH agonist protocol using rFSH derived from Chinese hamster ovary cell lines in conventional dosing have consistently indicated that the cohort of recruited follicles is slightly smaller with the GnRH antagonist protocol. A difference in oocytes of -1.0 (95% confidence interval [CI]: -1.8; -0.2) was observed in the largest randomised controlled trial⁷ which is in agreement with the difference of -1.1 (95% CI: -1.5; -0.6) in a Cochrane review including data from 27 randomised controlled trials.¹⁷

A phase 3b trial (000304)¹⁸ investigating efficacy and safety of FE 999049 with individualised dosing in subjects undergoing controlled ovarian stimulation for IVF or ICSI, following either a long GnRH agonist protocol or a GnRH antagonist protocol, showed a higher number of oocytes retrieved in the long GnRH agonist protocol compared with the GnRH antagonist protocol with a difference of 1.31 [95% CI: 0.22; 2.40]. The result is similar to those reported from previous trials with other gonadotropin preparations.^{7,19}

The present trial will evaluate the efficacy and safety of FE 999049 in a conventional dosing regimen, i.e. a standard starting dose fixed for the initial days of stimulation, followed by the possibility for subsequent dose adjustments, in a long GnRH agonist protocol in Chinese women undergoing controlled ovarian stimulation for IVF or ICSI.

